Non-inferiority study of immediate or delayed provisionalization at posterior healed sites using NobelParallel™ CC implants

STUDY PURPOSE AND RATIONALE

Dental implants are a widely used treatment option for the replacement of lost teeth due to trauma or oral diseases. The original protocol for placement of dental implants in edentulous spaces in the maxilla or the mandible was introduced more than thirty years ago and called for a two-stage approach, i.e., surgical placement of submerged dental implants and subsequent uncovering with abutment connection, prosthesis fabrication and functional loading approximately 6 months after (Brånemark et al., 1983). Today, the time between surgery and loading in a two-stage protocol has been commonly abbreviated to 3-4 months, while immediate implant provisionalization has emerged as a reliable and predictable option in cases of adequate osseous support, having similar survival and success rates to the two-step procedure (Esposito et al., 2009). Comparison of histological healing has demonstrated no significant differences in bone to implant contact between implants surgically placed according to a two-stage protocol and those immediately provisionalized (Piattelli et al., 1993). However, Esposito et al. (2009) also noted a substantial variability among the clinical protocols used in the studies carried out so far, and concluded that additional well-designed randomized controlled trials (RCTs) are needed to fully appreciate the clinical outcomes of immediate and early loading protocols.

The design of dental implants is a subject of continuous improvement, and implant manufacturers regularly introduce new products the use of which may result in accelerated soft and hard tissue healing, increased initial implant stability, and enhanced esthetic outcomes. The purpose of this randomized, controlled trial is to compare treatment outcomes when using a newly-introduced dental implant (NobelParallel™ CC) in a one-stage or a two-stage protocol. This new implant has the same titanium oxide surface coating (TiUnite®) and the same design principles of the parallel-walled NobelSpeedy Groovy™ implants, and an internal conical connection. The implant is marketed under the premarket notifications K050406 and K073142 (510 (k), Food and Drug Administration).

SUMMARY OF STUDY PURPOSE

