To compare two loading protocols using the new implant (NobelParallel™ CC) in posterior healed sites in two treatment arms: one in which the implant will be immediately provisionalized at the time of surgery, and another where the provisional crown will be delivered 3 months after the surgical procedure.

STUDY DESIGN AND STATISTICAL PROCEDURES OVERVIEW

This is a non-inferiority study of 12-month duration comparing the two treatment arms described above. Eligible patients with edentulous spaces at the maxillary or mandibular premolar/molar areas will be randomized to either an immediate provisionalization or a delayed provisionalization treatment arm. Patients in both treatment arms will receive their final fixed restoration at 4 months after surgery. The primary outcome of the study will be the radiographically assessed alveolar bone level change at the mesial and distal surface of the implant at 6 and 12 months after surgical placement. Secondary outcomes will include implant survival,

volumetric soft tissue changes, peri-implant probing depth, and implant stability by resonance frequency analysis.

POWER CALCULATIONS AND STATISTICAL ANALYSIS

Determination of sample size was based on anticipated differences in the primary outcome between the two treatment arms at 6 months (change in alveolar level from the time of implant placement). Based on similar data published in the literature (Esposito et al., 2013), we calculated with 1 mm bone remodeling in one treatment arm, and 1.5 mm bone remodeling in the second arm (i.e., expected mean difference between the two arms amounting to 0.5 mm). With a common standard deviation in both arms of 0.6 mm, the two-tailed effect size for a Student t-test (Cohen's d) amounts to 0.8333 mm. For an alpha error of 0.05 and power of 0.80, a total of 48 individuals in both arms is required for a two-tailed hypothesis. Thus, our plan is to enroll 50 individuals into the study.

Differences in the primary and secondary outcomes between the two treatment arms will be calculated using t-test for unmatched samples, after checking for data normality. Additional analyses will include regression models in which insertion torque (a measure of primary implant stability at the time of surgical placement) will be also used as a covariate along with treatment group allocation.

STUDY PROCEDURES

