Eligible participants (i.e., adults ≥ 18 years old in need of a dental implant at a posterior maxillary or mandibular region) who have been referred for dental implant treatment at the Clinics of the College of Dental Medicine will be approached by the study investigators and the aims of the study will be explained. Signed informed consent will be obtained.

All patients will be referred for limited field cone beam computer tomography to assess presence of adequate bone volume at the area of interest, according to standard clinic protocol. Alginate impressions will be obtained to fabricate diagnostic stone casts. A vacuum-formed stent will be manufactured in the laboratory to offer fixed reference points for longitudinal probing measurements, and a radiographic stent using polyvinyl siloxane interocclusal record material will allow standardized positioning of the radiographic holder to obtain periapical radiographs with the same projection geometry.

At the day of surgery (baseline), a computer-generated sequence will assign patients to either the one-stage or the two-stage treatment arm. In both arms, the implant will be placed flush with the bone crest, after flap elevation, according to standard treatment protocol. A periapical radiograph will be obtained immediately after completion of surgery.

Patients in the one-stage group will receive a temporary acrylic crown manufactured chair-side at the same visit. Care will be taken to relieve the crown from occlusal and laterotrusive contacts. The distance from the soft tissue margin to the occlusal stent will be measured using a periodontal probe at six sites around the implant (mesiobuccal, midbuccal, distobuccal, mesiolingual, midlingual and distolingual) at the time of post-surgical follow-up, 1-2 weeks after surgery.

At three months after implant surgery, patients in the two-stage group will have the implant uncovered after punching the oral mucosa, according to standard protocol. An acrylic temporary crown will be delivered. Soft tissue margin assessments measurements will be carried out, as described above, will be carried out at the time of post-surgical follow-up, 1-2 weeks after surgery.

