2. Measurements of soft tissue margin from a vacuum-formed stent at 6 sites per tooth (obtained at the day the provisional crown is delivered, i.e. at the post-operative visit 1-2 weeks after implant placement in the one-stage treatment arm, or at the post-operative visit 1-2 weeks after implant uncovering in the two-stage arm).
3. Probing depth measurements around the implant (at 4 and 12 months).
4. Volumetric assessments, based on digitally super-imposed casts (obtained at screening, 4 months and 12 months).
5. Resonance frequency analysis measurements using a Ostell™ device (at 4 and 12 months). These are non-invasive measurements of implant stability.

STUDY DRUGS

N/A

STUDY INSTRUMENTS

The NobelParallel™ CC implant is a new implant that has the same titanium oxide surface coating (TiUnite®) and a parallel-wall body design similar to the NobelSpeedy groovy™ and a conical internal connection. Both the implant and its prosthetic components have regulatory clearance [510(k)] by the Food and Drug Administration.

ADDITIONAL DATA COLLECTION

We will collect and review standard medical and dental history forms to confirm eligibility (age 18 years or older, participants who are systemically healthy or have controlled common systemic conditions, not pregnant, non-smoking or smoking <10 cigarettes/day, have no parafunctions or excessive occlusal forces, are not currently under orthodontic therapy, and have a stable occlusion). Intraoral photographs will be obtained for documentation purposes.

STUDY SUBJECTS

We will recruit 50 subjects among those referred to the College of Dental Medicine for tooth replacement using a dental implant in a posterior maxillary or mandibular region (premolar/molar area).

ADDITIONAL INCLUSION CRITERIA

Age 18 or older

Healed extraction sockets (extraction carried out at least 3 months prior to recruitment)

Implant site free of infection

Systemically healthy patients or with controlled common systemic conditions

Adjacent teeth present both mesially and distally to the implant site

EXCLUSION CRITERIA

Pregnancy or intent to be pregnant over the next 12 months

Current smoking exceeding 10 cigarettes/day

Parafunctional habits/ excessive occlusal forces

Current orthodontic therapy

Uncontrolled hypertension (blood pressure over 160/100) or poorly-controlled diabetes (HbA1c>8%).

RECRUITMENT

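### The same-day crown has no primary-stability criterion or fallback: an implant with low stability is crowned as written, and withholding that crown is a deviation only the one-stage arm can have

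*Combined protocol and SAP*

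**What the plan says.** Under Study Procedures, allocation takes place on the day of surgery: "At the day of surgery (baseline), a computer-generated sequence will assign patients to either the one-stage or the two-stage treatment arm". Placement comes next in the text: "In both arms, the implant will be placed flush with the bone crest, after flap elevation, according to standard treatment protocol". The order of the two within the day is not stated outright, but assignment is described first. The crown rule for the one-stage arm is unconditional: "Patients in the one-stage group will receive a temporary acrylic crown manufactured chair-side at the same visit". The protection stated alongside it is "Care will be taken to relieve the crown from occlusal and laterotrusive contacts". Two-stage patients are uncovered and given a provisional crown at three months.

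Stability or bone support appears in four other places:

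- Study Purpose and Rationale: "immediate implant provisionalization has emerged as a reliable and predictable option in cases of adequate osseous support".
- Study Procedures: cone beam CT before surgery "to assess presence of adequate bone volume at the area of interest".
- Power Calculations and Statistical Analysis: in additional regression models, "insertion torque (a measure of primary implant stability at the time of surgical placement) will be also used as a covariate".
- Research procedures, resonance frequency item: "device (at 4 and 12 months). These are non-invasive measurements of implant stability".

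None of these is a rule for giving or withholding the crown. The primary comparison is an unpaired t-test, and no analysis population is stated.

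**The concern.** The rationale limits its support for immediate crowns to sites with adequate bone support, and the analysis section treats insertion torque as a measure of primary stability. The investigators therefore regard stability as relevant and expect a reading at surgery, yet nothing uses that reading to decide about the crown. CT assesses bone volume before surgery, not the stability of the placed implant. Resonance frequency is first measured at four months, after the decision has been made.

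When a one-stage implant has low primary stability, the operator can do one of two things:

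- Follow the text and crown it. The risk falls on the patient.
- Depart from the text and delay the crown. The patient then receives something close to the comparator's course, for a reason that changes treatment in one arm only. In the two-stage arm the crown waits three months anyway, so low stability at placement calls for no change of plan. That arm can have other deviations, such as a postponed three-month crown, but not this one.

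In a non-inferiority trial the second course matters because patients who receive the comparator's treatment pull the arms together.

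**Working it through.** **Inputs from the document** (Power Calculations and Statistical Analysis): difference 0.5 mm, common SD 0.6 mm, two-sided alpha 0.05, power 0.80, total 48, planned enrolment 50.

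**Assumptions:** 25 per arm (no ratio is stated); a non-inferiority margin of 0.5 mm (none is stated); the one-stage arm as the worse one (the plan does not say which arm has 1.5 mm); the number k of one-stage patients whose crown is withheld; and the two-stage mean for those patients.

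**Plan's own figure.** d = 0.5/0.6 = 0.833. The two-sample t-test needs 23.6 per arm, rounded up to 24, so 48 in total. This reproduces the plan. Power is 80.7% at 24 per arm and 82.3% at 25 per arm.

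**Standard error.** 0.6 × √(2/25) = 0.170 mm.

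**Crown withheld, patient analysed as randomised.** With share c = k/25, a true difference D appears as D(1 − c). The variance in the one-stage arm becomes 0.36 + D²c(1 − c); for D = 0.5 and k = 5 that is 0.36 + 0.25 × 0.2 × 0.8 = 0.40. Each row below was simulated with 400,000 trials, using a pooled t-test on 48 degrees of freedom and a one-sided 2.5% level for non-inferiority.

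True difference 0: the mean difference stays at 0.00 mm, and power to show non-inferiority stays at about 82% for every k from 0 to 5.

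True difference 0.5 mm, one-stage arm worse:

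| k of 25 | Difference seen (mm) | False non-inferiority | Two-sided power |
|---|---|---|---|
| 0 | 0.50 | 2.5% | 82% |
| 1 | 0.48 | 3% | 79% |
| 2 | 0.46 | 4% | 75% |
| 3 | 0.44 | 5% | 71% |
| 5 | 0.40 | 8% | 62% |

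The largest shift, 0.10 mm, is 0.10/0.17 = 0.6 of a standard error. At k = 1 it is 0.02/0.17 = 0.1.

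**Crown given as written.** If each of k such implants lost an extra 0.5 mm (assumed), the one-stage mean would worsen by 0.5k/25: 0.02, 0.04, 0.06 or 0.10 mm for k = 1, 2, 3 or 5. The trial would be measuring a true consequence of crowning everyone, so this is not an error in the estimate.

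**The case against.** The strongest case against is that the risk is already low and the figures are hypothetical. Sites have healed for at least three months and are free of infection. Bone volume is checked by CT, parafunction is excluded, the crown is relieved of contacts, and residents work under faculty supervision. The standard treatment protocol cited for placement is not reproduced and may contain a stability rule. No rate of low stability is given, so 0 or 1 of 25 is plausible. The false non-inferiority rates describe a test the document does not set out: they need an assumed margin, a true difference exactly at it, and the one-stage arm as the worse one.

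Most of this stands, and it limits the size of the point. It does not remove the omission. None of these safeguards says what to do with an implant of low stability, and an unwritten judgement that overrides the crown rule would still be an undocumented deviation in one arm.

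A reader might infer three stronger things, which the document does not support:

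- **That crowning unstable implants biases the comparison.** It does not; extra loss would be a true effect of the randomised policy.
- **That only the one-stage arm can depart from its crown schedule.** The two-stage crown can also be postponed. Only withholding the same-day crown for low stability at placement is peculiar to one arm.
- **That weak sites will be dropped from the one-stage arm and flatter it.** No text says such patients are dropped. The unstated analysis population is a separate gap.

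**Conclusion.** The point holds as a gap in the plan of minor to moderate severity. The safety part rests on the text alone: an implant with low primary stability still gets a same-day crown. The document gives no failure rate for such implants, so the size of that risk cannot be stated.

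The inferential part is conditional. There is no bias if the arms do not differ. If the one-stage arm is 0.5 mm worse, one withheld crown changes little, while five of 25 roughly triple the false non-inferiority rate and cost about 20 points of two-sided power. These results rest on the assumed margin, equal arms and assumed rates. The unstated order of assignment and placement does not affect the conclusion, since assignment after placement would still leave no written criterion.

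**What to change.** Place the implant, record insertion torque and a yes/no judgement against a criterion the investigators fix in advance, and only then open the assignment at the same visit. This ensures that the arm is hidden during placement and that torque is a pre-randomisation covariate. The planned regression already needs the torque reading, so the procedural cost is a protocol amendment and an assignment opened after placement.

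**Preferred:** randomise only implants that meet the criterion, treat the others by the delayed protocol, and report their number. The conclusion is then limited to implants suitable for either protocol. At an assumed 4, 8, 12 or 20% unsuitable, operating on 50 patients leaves 48, 46, 44 or 40 randomised. Keeping 50 randomised means 50/(1 − rate) = 52.1, 54.3, 56.8 or 62.5, so 53, 55, 57 or 63 operated on. Those 3 to 13 extra surgeries fall on the manufacturer's funds, because surgical costs are waived for patients.

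**If the sponsor wants no exclusions:** randomise everyone after the torque reading, write the delayed crown as the fallback for implants below the criterion, analyse all patients as randomised, and report the number of crowns withheld. This needs no extra surgery. The dilution shown above remains, but it comes from a written rule and is reported.

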At four months after implant surgery, patients in both arms will have a final fixture level impression according to standard protocol for fabrication of the final implant supported restoration (a full contour Zirconia abutment crown with an angulated screw channel), which will be delivered approximately 2 weeks later. Resonance frequency analysis measurements will be obtained to determine implant stability using an Ostell™ device. After delivery of the final restoration, a periapical radiograph will be obtained, soft tissue margin measurements will be carried out as described above, and peri-implant probing depths will be assessed at the same six sites. An alginate impression will also be obtained to produce a stone cast to be used in volumetric measurements.

At seven months after implant surgery, patients in both treatment groups will return for a follow up visit to reinforce oral hygiene and will receive oral prophylaxis.

At twelve months after implant surgery, patients in both treatment groups will return for a follow up visit to reinforce oral hygiene and to receive oral prophylaxis. Resonance frequency analysis measurements will be obtained to determine implant stability using an Ostell™ device. A periapical radiograph will be obtained, soft tissue margin measurements will be carried out as described above, and probing depths will be assessed at the same six sites around the implant. An impression will be obtained to produce a cast to be used in volumetric measurements. The 12-month examination will conclude the study visits.

Research procedures

1. Radiographic measurements of alveolar bone level mesial and distal to the implant (at baseline, four months and 12 months) will be carried out using the MIPACS software. The implant platform will be the reference point. Note that although the measurements will be carried out for the purposes of the study, periapical radiographs after completed surgery, at the time of delivery of the final restoration, and at 12-months post-surgery are standard protocol in implant dentistry. Thus, the study does not require any additional exposure to radiation beyond what is considered the standard of care.

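### The plan describes no masking to arm or visit for the film readings that form the primary outcome

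*Combined protocol and SAP*

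**What the plan says.** Study Design and Statistical Procedures Overview defines the primary outcome as "radiographically assessed alveolar bone level change at the mesial and distal surface of the implant at 6 and 12 months after surgical placement" and states the design: "This is a non-inferiority study of 12-month duration comparing the two treatment arms described above".

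Research procedures, item 1, lists films at baseline, four months and 12 months and says that the measurements "will be carried out using the MIPACS software. The implant platform will be the reference point". Study Procedures adds a radiographic stent so that projection geometry is the same at each visit. (The primary outcome is stated at 6 months while the film is listed at four; that is a separate matter.)

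On timing, Study Procedures says of the baseline film: "A periapical radiograph will be obtained immediately after completion of surgery". The one-stage arm receives a chair-side temporary crown at that same visit. The two-stage arm has its implant uncovered and crowned at three months. Both arms then get the same type of final restoration, and for the next film the text reads: "After delivery of the final restoration, a periapical radiograph will be obtained". The last film is at 12 months.

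No section mentions masking of patients, operators, film readers or the analyst. No reader is named, and no coded or random reading order is described. Study numbers appear under Confidentiality of the Data, for linking records. That section also gives the principal investigator and co-investigators access to the records.

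**The concern.** Placing the bone-level landmark on a periapical film leaves room for judgement. The stent standardises the image but not the person measuring it. The treatments look different to everyone in the clinic, and nothing written in the plan keeps that knowledge from the reader. The plan could be followed to the letter with readings made by someone who knows the arm.

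The stake is a systematic shift in the difference between arm means, which a larger sample does not remove. The declared aim is non-inferiority, so readings drawn toward similarity would favour the claim under test. Readings drawn apart would do the opposite, or would create a difference.

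**Working it through.** **Inputs.** All come from Power Calculations and Statistical Analysis unless marked.
- Planning difference: "expected mean difference between the two arms amounting to 0.5 mm".
- Spread: "With a common standard deviation in both arms of 0.6 mm".
- Error rates: "For an alpha error of 0.05 and power of 0.80", two-tailed; 48 required, 50 to be enrolled.
- Assumed: 1:1 allocation (no ratio is stated), hence 25 per arm with no dropout.
- Assumed: reader shift b of 0.05, 0.1 or 0.2 mm. The documents give no value.
- Assumed, for one column only: a margin of 0.5 mm. No margin is stated.

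**The plan's own figure.** d = 0.5/0.6 = 0.8333. The normal approximation gives n per arm = 2 × (1.960 + 0.842)² / 0.8333² = 22.6, so 23 per arm or 46 in total. The exact noncentral t gives power 0.789 at 23 per arm and 0.807 at 24, so 48 in total reproduces. With 25 per arm, power is 0.823. None of this is in dispute, and masking leaves it unchanged.

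**Precision.** SE = 0.6 × √(2/25) = 0.170 mm on 48 degrees of freedom. The two-sided 5% critical value is 2.011, so the 95% half-width is 2.011 × 0.170 = 0.341 mm.

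**Scenario A: the shift shrinks a true difference of 0.5 mm.**
- Power of the planned two-sided t-test uses noncentrality (0.5 − b)/SE. At b = 0.1 this is 0.4/0.170 = 2.36, against 2.95 with no shift.
- False non-inferiority, if the margin were 0.5 mm and the true difference lay on it, is the probability that a noncentral t with noncentrality b/SE exceeds 2.011. At b = 0.1 the noncentrality is 0.59.

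**Scenario B: the shift creates a difference where none exists.** Two-sided type I error uses noncentrality b/SE.

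| Assumed b (mm) | A: power for 0.5 mm | A: false non-inferiority (0.5 mm margin assumed) | B: two-sided type I error |
|---|---|---|---|
| 0 | 0.823 | 2.5% | 5.0% |
| 0.05 | 0.738 | 4.7% | 6.0% |
| 0.1 | 0.637 | 8.3% | 8.9% |
| 0.2 | 0.410 | 21.0% | 21.1% |

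A and B are different biases and their consequences do not add up. Drift toward no difference lowers power; it cannot inflate the two-sided type I error.

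**Where the arm could be seen.** The baseline film may show it, if arm-specific hardware is in place when the film is taken. Study Procedures describes that film before it describes the one-stage crown and does not settle the order. The two later films show the same type of restoration in both arms, so there the risk comes from recognising the patient or knowing the allocation.

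**The case against.** The strongest reply is that the room for bias is limited. Implants in both arms are set level with the bone crest and the platform is the reference point, so the intended baseline reading is near zero in both. Bone change appears on the later films, where the hardware need not reveal the arm. The crown may not be on the baseline film at all, and the stent controls geometry. All of this stands as a reason to expect a modest bias. It does not remove the gap: the baseline reading is still measured and enters every change score, and a reader who knows the patient or the allocation needs no cue from the film.

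The shift sizes and the margin are assumptions. That also stands, so the figures show sensitivity and are not estimates.

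A reader might infer that investigators who know the arm will measure the films, or that the films plainly reveal the arm. The documents support neither: they are silent on the reader, and only the baseline film may carry a cue. A reader might also infer that an independent reader without access to the allocation is already available. Residents place and restore the implants under faculty supervision and there are co-investigators, so this is plausible, but it is not documented.

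Finally, covering the image right up to the platform could add measurement error at the reference line. That is fair, and the fix allows for it.

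**Conclusion.** The point holds in a limited form. The plan contains no masking to arm or visit for its primary measurement, and the arms are visibly different to staff and patients. Reader expectation can therefore shift the primary result; nothing in the documents shows that it will, or in which direction. The plan does not even say which arm is expected to lose 1.5 mm.

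A shift of 0.1 mm, one fifth of the planning difference, would matter: power 0.82 to 0.64, or, in the separate scenario of a created difference, type I error 5% to 8.9%. These two results rest on 25 per arm, an SD of 0.6 mm and the assumed shift. The rise in false non-inferiority from 2.5% to 8.3% also needs an assumed 0.5 mm margin. The change should be made before any film is read, because unmasked readings can be put right only by reading the films again under masking.

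**What to change.** Add to Research procedures, item 1:
- All films are exported under a random code, with no patient, arm or visit label.
- Hardware coronal to the platform that could show the arm is covered, in the same manner for both arms, leaving the platform edge and the adjacent crestal bone fully visible.
- All films are read in random order, in one batch, after the last 12-month visit and before the codes are linked to allocation.
- Where possible, the reader is an existing team member who did not treat the patient.

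If no such person is available, the first three steps still remove most cues.

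The cost is protocol wording and a few hours of image preparation, and the study readings wait until the end of the trial. No film or visit is added, since item 1 already treats all three films as standard care, and the sample size does not change.

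### Does item 2 of the Research procedures contradict the visit schedule on when, and how often, the soft tissue margin is measured?

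*Combined protocol and SAP*

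**What the plan says.** Item 2 of the Research procedures describes the margin readings, at six sites, as "obtained at the day the provisional crown is delivered, i.e. at the post-operative visit 1-2 weeks after implant placement in the one-stage treatment arm". For the two-stage arm it names the corresponding visit after the implant is uncovered. It lists no later reading.

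Study Procedures sets out the visits:

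- One-stage arm, day of surgery: "Patients in the one-stage group will receive a temporary acrylic crown manufactured chair-side at the same visit". The margin is measured at the follow-up one to two weeks later.
- Two-stage arm, month 3: the implant is uncovered, and "An acrylic temporary crown will be delivered". The margin readings "will be carried out at the time of post-surgical follow-up, 1-2 weeks after surgery". The Summary of Study Purpose agrees on the month, describing this arm as "another where the provisional crown will be delivered 3 months after the surgical procedure".
- Both arms, about two weeks after the 4-month impression: "After delivery of the final restoration, a periapical radiograph will be obtained, soft tissue margin measurements will be carried out as described above".
- Both arms, month 12: "A periapical radiograph will be obtained, soft tissue margin measurements will be carried out as described above, and probing depths will be assessed".

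The other entries in the Research procedures list carry their later dates; item 3, for example, reads "Probing depth measurements around the implant (at 4 and 12 months)". The design overview names bone level change as the primary outcome. The secondary outcomes are implant survival, volumetric soft tissue change, probing depth and implant stability. The margin distance is not among them.

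**The concern.** On a first reading item 2 conflicts with the schedule in two ways. It equates the crown-delivery day with a visit that, in the one-stage arm, plainly comes one to two weeks after the crown. It is also the only one of the five entries that omits the later time points.

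If staff worked from item 2 alone, each patient would have a single margin reading. The two arms' readings would fall about three months apart in time since placement, with no visit in common and no follow-up value from which to compute a change. Under the visit schedule there are two shared visits, so a like-for-like comparison is possible. The plan also does not say which reading is the reference for margin change, or whether that change is compared between arms.

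**Working it through.** The plan gives no figure to reproduce. The check sets the sections side by side and then counts readings and intervals.

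**Day of the first reading** (1-2 weeks = 7 to 14 days; 7/30.44 = 0.23 and 14/30.44 = 0.46 months)

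| | Crown delivered | First margin reading, Study Procedures | Visit named in item 2 |
|---|---|---|---|
| One-stage | month 0 | 0.23-0.46 months | 1-2 weeks after placement |
| Two-stage | month 3 (inferred) | 3.23-3.46 months | 1-2 weeks after uncovering |

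The last two columns agree. Only item 2's reference to the crown day is out of place, and no visit in Study Procedures schedules a margin reading on that day. The two-stage crown day is inferred from the order of the paragraph and from the Summary of Study Purpose; only the one-stage text states that the crown is given at the same visit. Study Procedures does not say whether the two-stage follow-up is counted from placement or from uncovering. The sentence follows the uncovering step, and item 2 says uncovering, so here item 2 settles the question.

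Moving the reading to the crown day would not alter the offset between arms: 3 - 0 = 3 months on the crown day, and 3.23 - 0.23 = 3 months at the follow-up visit.

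**Number of readings**

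- Item 2 alone: 1 time point x 6 sites = 6 per patient.
- Study Procedures: 3 time points x 6 sites = 18 per patient.

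Item 2 does not say that its visit is the only one. Study Procedures orders the other two readings in both arms, and it describes the stent as giving fixed reference points for longitudinal measurement, which presupposes repeat readings. The list is also loose elsewhere: item 3 gives probing depth at 4 months, whereas the schedule takes it at final-restoration delivery about two weeks later. It reads as a summary of the schedule.

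**Intervals, if the first reading were the reference**

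Final restoration = 4 + 0.46 = 4.46 months.

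- One-stage: to final restoration, 4.46 - (0.23 to 0.46) = 4.00-4.23 months; to month 12, 12 - (0.23 to 0.46) = 11.54-11.77 months.
- Two-stage: to final restoration, 4.46 - (3.23 to 3.46) = 1.00-1.23 months; to month 12, 12 - (3.23 to 3.46) = 8.54-8.77 months.
- Between the two shared visits, either arm: 12 - 4.46 = 7.54 months.

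The unequal intervals arise only if an analyst takes the first reading as the reference, which the plan nowhere says. They describe a hypothetical analysis and do not measure the wording problem.

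**Use of the measurement.** Power Calculations and Statistical Analysis applies t-tests to the primary and secondary outcomes. The sample size (48 required, 50 planned) rests on bone level change. Volumetric change comes from superimposed casts (item 4: screening, 4 and 12 months), not from the stent-to-margin distance. None of these uses the margin readings.

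**The case for a change.** The best case for a change is that the protocol states no order of precedence between Study Procedures and the Research procedures list. Item 2 is the dedicated entry for this measurement, and its four neighbours all give their 4- and 12-month points, so the omission cannot be put down to house style. A correction would cost only words, and one sentence on the reference reading would stop an analyst from comparing changes over unequal intervals.

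The textual part stands: item 2 is loosely written and could be tidied whenever the document is next edited. The harm does not follow. It needs staff to ignore two express instructions in the schedule, at visits where the radiograph and probing depths are due anyway.

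The added analysis sentence is a different matter, because it would fix a method for a comparison that the plan never announces, and reasonable statisticians would choose differently. Margin position at 12 months is protected by randomisation, but it carries each patient's stent and tooth dimensions and may be noisy. Change from final restoration removes that patient-specific component but uses a post-randomisation reference. Neither choice is forced by the documents.

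**Conclusion.** No change is needed. Item 2 contains a clerical slip (the crown day) and an omission (two later readings), and Study Procedures supplies what is needed to read both correctly. The gap in the list is 12 of 18 scheduled site readings per patient (18 - 6 = 12), all of which the schedule itself orders. The effect on the primary outcome, the named secondary outcomes, their tests and the sample size is nil, because none of them uses the margin distance.

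This rests on three assumptions: staff follow the visit schedule; the two-stage crown is delivered at uncovering, as the text most naturally reads; and the margin readings remain descriptive. If a comparison between arms were reported, an analyst would see that the first readings are three months apart in time since placement and that both arms share the final-restoration and 12-month visits. That gap can be filled sensibly without a prescribed rule.
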